2A. Lactogenesis

Lactogenesis is a two-stage physiologic process of developing the ability to secrete milk that starts from 16th week of pregnancy and continues after delivery regardless of the birth outcome (Lawrence 2011). Stage I lactogenesis (secretory initiation) takes place during the second half of pregnancy where high level of estrogen, progesterone, and prolactin stimulate anatomic growth of breasts. Prolactin initiates lactose synthesis in alveolar cells which remains inhibited by high levels of estrogen and progesterone secreted by the placenta during this stage in pregnancy.

Stage II lactogenesis (secretory activation) starts after the removal of the placenta with a rapid drop in progesterone. The fall in progesterone removes the antagonizing effect on prolactin to start milk production resulting in swelling of the breasts and milk production that starts postpartum days 2-3. Breast engorgement happens when lactation supply exceeds what is expressed from breasts.

Prolactin is a peptide synthesized in the anterior pituitary and is both positively and negatively regulated. Regular expression of milk and nipple stimulation triggers prolactin release. Dopamine released by the hypothalamus acts as an inhibitory factor to prolactin release by stimulating D2 receptors in the anterior pituitary. The normal range in non-pregnant, non-lactating assigned female at birth is 5-23 μ g/L.

In absence of physical stimulation, lactation eventually stops. Among those who do not breastfeed, milk leakage and breast pain begin between 1 to 3 days postpartum and engorgement begins between 1 and 4 days postpartum, all symptoms peaking 3-5 days postpartum and continuing up to three weeks. (Spitz, 1998, Melis 1988).

Figure 1. Stage I lactogenesis (secretory initiation) takes place during the second half of pregnancy where high level of estrogen, progesterone, and prolactin stimulate anatomic growth of breasts. Stage II lactogenesis (secretory activation) starts after the removal of the placenta with a rapid drop in progesterone. The fall in progesterone removes the antagonizing effect on prolactin. (Love 1990)

2B. Lactogenesis in second-trimester abortion or loss

Breast pain following second-trimester abortion is common. In a prospective, longitudinal study following women after a 14-20 week fetal loss of abortion found on day 3 post-procedure, 50% reported breast tenderness, 45% engorgement, and 20% milk leakage (Hagey 2020).

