The safety of bromocriptine for lactation inhibition was called into question in 1984, when the US Food & Drug Administration (FDA) called attention to reports of postpartum hypertension, seizures, and strokes associated with the use of bromocriptine. (Rayburn 1996). While no studies found an increased incidence of these events compared to placebo or anticipated postpartum incidence, the FDA ultimately asked the manufacturer in 1990 to voluntarily stop selling bromocriptine as a lactation suppressant.

In addition to the existing data showing safety of cabergoline, there is theoretic biologic plausibility as to why cabergoline is better tolerated than bromocriptine. Cabergoline has a greater affinity for D2 receptors, longer plasma half-life, and flat plasma drug concentration resulting in a shorter required duration of therapy compared to bromocriptine. (Rains 1995) Notably, in Canada, the UK, and France, cabergoline has an approved indication for the prevention of physiologic postpartum lactation.

3. Research Questions

We are aiming to answer whether cabergoline is superior to placebo at preventing breast symptoms after secondtrimester abortion or loss. The goal is to improve patient experience and establish a standard of care for lactation inhibition after second-trimester abortion or loss.

Our primary outcome is breast symptoms on Day 4 post-abortion/ post fetal expulsion. Secondary outcomes include initiation of milk secretion, satisfaction, acceptability, and side-effects.

We will test the following hypotheses:

1. A smaller proportion of those receiving cabergoline will report breast symptoms on Day 4 compared to placebo.

2. Prolactin levels will be significantly lower on Day 4 in those receiving cabergoline compared to placebo.

3. The proportion of participants ever reporting secretion of milk within 14 days post-procedure will be lower in those receiving cabergoline compared to placebo.

4. Participants receiving cabergoline will be more satisfied with their post-procedure breast symptoms compared to those receiving placebo.

5. Side-effects will occur in less than 10% of patient and not differ between those receiving cabergoline compared to placebo.

4. Methods

4A. Research Design and General Methodological Approach

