The study is designed as a prospective double-blinded, placebo-controlled, superiority trial to evaluate cabergoline's role in relieving breast engorgement after second-trimester abortion or fetal demise. Breast symptoms will be defined by the validated Bristol Breast Inventory score. (Bristol 1966)

A superiority design was selected as cabergoline is fairly expensive with possible side-effects. For this study to be practice-changing, cabergoline needs to demonstrate clear superiority over placebo.

Day #0 - Pre-operative visit/Cervical preparation visit

Eligible patients who are scheduled for an abortion or are diagnosed with an intrauterine fetal demise between 18–28 weeks gestation will be approached to enroll in the study. A research staff member will obtain informed consent and randomization will occur. Basic demographic information will be collected and entered into REDCap by a research coordinator. (Harris 2009) Standard demographics, gender identity, prior breastfeeding/ chestfeeding experience, and prior breast surgery will be asked of participants. A baseline Bristol Breast Inventory questionnaire will be performed to establish existing breast symptoms related to pregnancy followed by a 7-point Likert bother scale.

Standard counseling regarding medical or surgical management will be provided, as applicable. A complete history and physical will be performed. If an ultrasound report is not available to confirm gestational age dating, an informal, bedside abdominal ultrasound will be performed to determine gestational age. All patients will receive mifepristone 200mg PO. Those choosing D&E will also have osmotic dilators placed. Participants over 22 weeks with a viable intrauterine pregnancy will receive feticidal injection with either lidocaine or digoxin as is standard practice at these sites. Standard of care antibiotics for prophylaxis will be provided, if indicated.

Day #1 – Procedure/ Induction day

Dilation and evacuation (D&E) are done in the outpatient gynecology clinic or ambulatory surgical center, depending on patient preference and other medical considerations. All participants will receive pre-procedure misoprostol 90 minutes prior to procedure as is standard practice at our site.

Those seeking medical abortion or those with fetal demise over 24 weeks gestation will be admitted to Labor & Delivery where they will receive repeat doses of misoprostol 400 mcg buccal every three hours until fetal expulsion occurs.

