Those in the serum sub-study will have a prolactin level drawn at the time of intravenous (IV) insertion. Rhogam will be provided if indicated.

Within 4 hours of fetal expulsion and prior to discharge, the study coordinator will distribute the study drug or placebo as randomized on Day #0. All participants will receive standard information on support bras, analgesics, and cold compacts.

Days # 2-14 - Follow-up

Electronic, online surveys regarding breast symptoms using the Bristol Breast Inventory, 7 point Likert Scale to assess bother of symptoms, current bleeding profile (Janssen 1995) and side-effects will be collected on Days 2, 3, 4, 7, 14. Additionally, participants will be asked on Day 14 to rate overall acceptability of the protocol, likelihood to recommend to a friend, and willingness to pay. Surveys will be sent via text message over RedCap at 08:00. (Friedlander 2020) A phone call will be made to participants between 17:00-20:00 if the survey is not completed that day. Day 14 survey will include measures of willingness to pay and overall satisfaction.

A substudy of 10 patients enrolled at Stanford (5 cabergoline, 5 placebo) will return to Stanford laboratories for repeat serum prolactin levels on Day 2, 4, 7, 14.

An electronic gift card will be sent to the participant after 14 days. Participants will receive **\$** per survey completed with a **\$** bonus for completing all five surveys on-time for a maximum of **\$** for full participation. Those participating in the serum prolactin sub-study will receive **\$** per phlebotomy session with a bonus **\$** for completing all lab draws on the appropriate day for a maximum of **\$** for full participation. With consent, the gift card will be distributed by e-mail or mobile phone number via Amazon. For patients who prefer a physical gift card, it will be mailed to their reported address. Participants will have the opportunity to forego gift certificate and donate funds to a reproductive health organization.

4B. Criteria for selection of subjects

Inclusion:

Pregnant people, ages 18 years or older

Intrauterine pregnancy between 18/0-28/0 weeks of gestation age (by ultrasound dating performed prior to or same day of enrollment visit)

Consented for an induced, elective abortion or undergoing induction for demise

English or Spanish speaking

Able to consent for a research study, literate in English or Spanish

Willing to comply with study procedures and follow-up

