Stanford University has a license for the RedCap data management system. (Harris 2009) REDCap is a web-based application that is secure, reliable, and HIPAA-compliant for storing research study data. REDCap is designed with built-in features to address confidentiality and compliance requirements. Electronic, online surveys will be sent via text message over RedCap on Days 2, 3, 4, 7, 14. Data associated with patient health identifiers (PHI), including the signed informed consent, will be collected electronically. REDCap allows for easy data download into SAS or other statistical software programs. No data will be collected on paper forms. SAS OnDemand will be used for data analysis. Data will be analyzed with parametric or non-parametric statistical tests, as appropriate. Stratified analysis and logistic regression will be performed to assess demographic characteristics as predictors of breast symptoms and associate distress.

A Data and Safety Monitoring Committee (DSMC) will be used given that the use of cabergoline for lactation inhibition is a new and unfamiliar intervention and limited data exists for this use. A DSMC will be formed to monitor the progress of the study and review any of the following events under the Data and Safety Monitoring Plan: (i) Adverse events and/or serious adverse events will be recorded in our data collection tool, REDCap (ii) The research coordinator will be responsible for directly monitoring the data and compliance with the protocol. All events will be immediately reported to the principal investigator/sponsor. The sponsor will be responsible for reporting any adverse or serious adverse events to the DSMC members and IRB (iii) Serious adverse events and unanticipated problems will be reported immediately to the monitoring committee and any events of stroke, hospitalization for hypertensive emergency, hospitalization for psychiatric condition will lead to immediate termination of the study (iv) Side-effects that are common according to the FDA package insert including nausea/vomiting, headache, dizziness, orthostatic hypotension, constipation, abdominal pain, fatigue will be reported to the IRB by the principal investigator. All adverse events will be summarized with special attention to events that may be related to the study drug.

5. Study Population

Number of Subjects and Statistical Power

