Incidence of symptomatic breast engorgement after second-trimester abortion has been reported to occur between 50-91% of individuals (Hagey 2020, Anderson 1990). In prior studies of term lactation inhibition using

cabergoline 1 mg, complete absence of lactation was noted in 78-100% of study subjects (European 1991, Mellis 1998, Giorda 1991, Caballero 1991). We estimate that 41 subjects in each group are required to show a 30% decrease in those reporting breast symptoms compared to the control group, with a power of 0.8 and an alpha of 0.025 (planned interim analysis). We plan to recruit 100 subjects, anticipating 10% missing data and loss to follow up.

Based on the prior RCT comparing bromocriptine to placebo after second-trimester abortion, the mean serum prolactin level in the placebo group was $44\pm8 \mu g/L$ on Day 4 and $12.2\pm2 \mu g/L$ in the bromocriptine group (Andersen 1990). The upper-limit of normal for a non-lactating female-assigned at birth is 23 $\mu g/L$. We will need 8 patients to have a 90% chance of detecting, at the 5% significance level, a decrease in serum prolactin from 44 in the control group to 23 in the experimental cabergoline group. We will recruit 10 subjects, anticipating 20% loss to follow up and missing data.

Locations

Patients will be recruited at Stanford Gynecology Clinic in Palo Alto, CA. Stanford University is a large tertiary care center with patients referred from the seven Perinatal Diagnostic Centers (PDCs) across Northern California with fetal anomalies as well as local practices and Planned Parenthood Mar Monte California. Medicaid covers abortion care through 23/6 weeks. In 2019, we performed 72 abortions between 18/0 and 23/6 weeks gestation at Stanford University and the Lucille Packard Childrens Hospital admitted an average of 1 patient each month for medical abortion or fetal demise between 18-28 weeks gestation.

6. Timeline

With an anticipated 66% enrollment, we anticipate enrollment to take 19 months.

| Year 1 | Sept-20 | Oct-20 | Nov-20 | Dec-20 | Jan-21 | Feb-21 | Mar-21 | April-21 | May-21 | June-21 | |
|---------------------|---------|--------|---------|--------|--------|--------|--------|----------|--------|----------|--------|
| Consent development | х | Х | | | | | | | | | |
| Survey development | Х | Х | | | | | | | | | |
| IRB review | | Х | х | х | | | | | | | |
| Recruitment | | | | | Х | Х | х | Х | Х | Х | |
| Data collection | | | | | х | х | х | х | х | х | |

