| Year 2 | July-21 | Aug-21 | Sept-21 | Oct-21 | Nov-21 | Dec-21 | Jan-21 | Feb-21 | Mar-21 | April-21 | May-21 |
| Recruitment | Х | Х | х | х | х | х | х | х | х | | |
| Data collection | Х | Х | х | х | х | х | х | х | х | | |
| Interim analysis | Х | | | | | | | | | | |
| Data analysis | | х | | | | | | | Х | х | |
| Manuscript | | | | | | | | | | х | Х |

7. Use of Research Results

We aim to present the findings at the ACOG Annual Clinical Meeting in spring 2022 as we believe these data will be broadly applicable for MFMs and generalist obstetricians caring for second-trimester losses in additional to Complex Family Planning subspecialists. We also plan to publish the findings in a peer-reviewed journal and work with the Society of Family Planning and ACOG on guideline development. Results will also be used to inform future studies including a cost-effectiveness analysis.

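### The baseline Bristol score has no stated role in the Day-4 comparison; adjusting for it is a cheap precision gain of unknown size that needs a penalised fit

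*Combined protocol and SAP*

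**What the plan says.** - **Baseline (section 4A, Day #0).** "A baseline Bristol Breast Inventory questionnaire will be performed to establish existing breast symptoms related to pregnancy". The purpose given is descriptive.
- **Timing of dosing (section 4A, Day #1).** After fetal expulsion, "the study coordinator will distribute the study drug or placebo as randomized on Day #0". The score therefore precedes dosing, and the trial is double-blinded.
- **Primary comparison (section 3, hypothesis 1).** "A smaller proportion of those receiving cabergoline will report breast symptoms on Day 4 compared to placebo". Section 4A defines symptoms by the Bristol score but gives no cut-off.
- **Analysis (section 4F).** No primary test is named; the choice between parametric and non-parametric tests is left open. The one regression planned is this: "Stratified analysis and logistic regression will be performed to assess demographic characteristics as predictors of breast symptoms and associate distress". A Bristol score is not a demographic characteristic, and that sentence is about predictors of symptoms, not the effect of treatment.
- **Size (section 5).** 41 per group to show "a 30% decrease in those reporting breast symptoms compared to the control group, with a power of 0.8 and an alpha of 0.025", and "We plan to recruit 100 subjects, anticipating 10% missing data and loss to follow up". The Brief Summary gives 32 per group, alpha 0.05 and 30% loss.
- **Timing of the look (section 6).** The row "Interim analysis" is marked for July-21.

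Nowhere does the baseline score appear as a covariate, a stratification factor or part of the Day-4 case definition.

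**The concern.** A baseline measurement on the outcome's own instrument is usually the first candidate covariate. Here it will already have been collected, treatment cannot have affected it, and the trial is small and recruits at one centre. If baseline predicts Day 4, leaving it out forgoes precision that would otherwise have to be bought with participants. Timing matters too. Because 4F leaves the choice of test open, a decision to adjust that is made after data have been seen would be open to the charge of selection.

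**Working it through.** **1. The plan's own figure.** For two proportions, pooled variance, 1:1, two-sided:

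n = [z(1-α/2)·√(2p̄(1-p̄)) + z(0.8)·√(p1(1-p1) + p2(1-p2))]² / (p1-p2)²

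The documents state no control rate (they cite 50-91%) and do not say whether the 30% is absolute or relative. Taking 30 points and 90 vs 60%:
- α = 0.05: (1.960×0.6124 + 0.8416×0.5745)² / 0.09 = 31.5, so 32 per group, as in the Brief Summary.
- α = 0.025: (2.241×0.6124 + 0.8416×0.5745)² / 0.09 = 38.3, so 39, close to the stated 41. At 88 vs 58% the formula gives exactly 41.

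**2. Setting for the check.** 100 recruited less 10% leaves 90, or 45 per arm; two-sided alpha 0.025.

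Assumed, because the documents are silent:
- control rates of 90, 80 or 70%, with a 30-point difference;
- correlation between the underlying baseline and Day-4 scores of 0, 0.3 or 0.5;
- the share scoring zero at baseline, either none or 70%.

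The range starts at zero for a reason. Section 2A says "Stage II lactogenesis (secretory activation) starts after the removal of the placenta with a rapid drop in progesterone", so symptoms on Day 4 may owe little to those on Day 0.

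**3. Power.** Scores were drawn as bivariate normal and Day 4 was cut to the stated rates. A logistic likelihood-ratio test was run with and without baseline, 20,000 trials per cell. The Monte Carlo error of a gain is 0.1-0.3 points.

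| Rates | Unadjusted to adjusted, corr. 0 | 0.3 | 0.5 | Gain in points with 70% at zero, corr. 0.3 / 0.5 |
|---|---|---|---|---|
| 90 vs 60% | .890 to .885 | .889 to .901 | .892 to .930 | 0.1 / 1.2 |
| 80 vs 50% | .792 to .790 | .793 to .818 | .796 to .858 | 0.7 / 2.5 |
| 70 vs 40% | .750 to .749 | .749 to .776 | .752 to .826 | 1.3 / 3.9 |

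If 30% is a relative reduction (91 vs 64, 90 vs 63, 80 vs 56, 70 vs 49%), the changes are -1.0 to +0.4, +0.9 to +2.9 and +4.1 to +7.9 points at correlation 0, 0.3 and 0.5.

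**4. In participants.** With no floor at zero, the ratio of the SD of the standardised risk difference to that of the crude one is 1.005-1.007 at correlation 0, .976-.985 at 0.3 and .923-.943 at 0.5. Then 90×(1/ratio² - 1) gives:
- correlation 0: about -1;
- correlation 0.3: 90×(1/.985² - 1) = 2.8 to 90×(1/.976² - 1) = 4.5;
- correlation 0.5: 90×(1/.943² - 1) = 11.2 to 90×(1/.923² - 1) = 15.6.

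**5. Does the gain carry over to a risk difference?** A separate simulation with a logistic data model, 41 per arm and 90 vs 60% gave adjusted power of .855, .867, .889 and .919 by likelihood ratio as the covariate strengthened. By the standardised risk difference it gave .857, .870, .891 and .920. The two agree.

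**6. Type I error (nominal 0.025).** Likelihood-ratio tests: .0263-.0351 unadjusted and .0267-.0360 adjusted, a difference of -0.16 to +0.09 points. Standardised risk difference: .0261-.0296. Adjustment is not the source of the liberality.

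**7. Fitting problems.** If every participant with a non-zero baseline is symptomatic on Day 4, the ordinary logistic slope has no finite estimate. With 70% at zero and correlation 0.5:

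| Setting | This pattern occurs | Ordinary fit reported as not converged |
|---|---|---|
| 45/arm, 90 vs 60% | 6.3% | 3.7% |
| 45/arm, 80 vs 50% | 1.3% | 0.7% |
| 45/arm, 80 vs 80% | 21% | 12.9% |
| 45/arm, 90 vs 90% | 59% | 36% |
| 20/arm (assumed interim), 90 vs 60% | 30% | not run |
| 20/arm (assumed interim), 80 vs 50% | 15% | not run |

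With a Firth fit substituted on failure, type I error of the standardised risk difference was .0271 and .0253 in the two no-effect settings. Power was .910 against .895 crude (90 vs 60%) and .827 against .793 (80 vs 50%).

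**The case against.** **The bigger gap lies elsewhere.** 4F names no primary test and 4A no Day-4 cut-off, so an unadjusted primary analysis is an inference, not something the plan commits to. This stands. The recommended model also needs the missing cut-off, so the two should be settled together.

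**The benefit may be close to nil.** In the scenario nearest the stated sample sizes (90 vs 60%), unadjusted power is already about 0.89 against a target of 0.80. Adjustment there adds 1.2 points at correlation 0.3, or 0.1 with 70% at zero. This also stands, and it is why the point is only worth considering. At 80 vs 50% and 70 vs 40%, unadjusted power is slightly below 0.80 and a gain would be more useful.

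**Adjustment is not free.** A reader might infer that adding a covariate costs nothing. The fitting failures above show otherwise: if many score zero at baseline and symptoms are common in both arms, the penalised fit could be the main analysis and not a rare fallback. The problem is worse at a small interim, whose size the documents do not state.

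**The type I comparison depends on the comparator.** Against an unadjusted Pearson chi-square (0.020-0.029 in simulation), the standardised risk difference (0.024-0.032) is slightly more liberal. Part of any apparent power gain over that test is therefore not real. The table above avoids this by comparing likelihood-ratio tests with each other.

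**Conclusion.** The omission is real, and pre-specifying adjustment is a worthwhile but modest improvement. At 45 per arm and an assumed 30-point difference, power changes by about -0.5 to 0 points at correlation 0, +1 to +3 at 0.3 and +4 to +7 at 0.5, roughly halved or less with 70% at zero. The correlation, the control rate, the reading of 30% and the baseline distribution are all assumptions.

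Two stronger readings are not supported. A reader might infer that an unadjusted comparison is biased or invalid; under randomisation it is neither. A reader might also infer that symptoms present before dosing erode the planned power. Section 5 words the decrease as one among all those reporting symptoms, and nothing in the documents shows such an erosion.

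**What to change.** In 4F, before the interim analysis, state that:

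1. The Day-4 primary outcome is yes/no on the Bristol score, with the cut-off given.
2. The primary model is logistic, on arm plus the baseline Bristol score as a single covariate in a fixed form (continuous score or any symptom, chosen now).
3. The standardised risk difference and its confidence interval decide success. The level matches the final alpha and the variance method is named (for example bootstrap or delta method), including after a penalised fit.
4. A Firth-penalised fit is used by a written rule, or from the outset, at both the interim and final analyses.
5. The crude difference in proportions is a sensitivity analysis.

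**Cost.** SAP wording and some SAS programming for the standardisation, its variance and the penalised fit. No new data are needed. If baseline proves uninformative, up to about 0.5 points of power are lost (about 1.0 if the 30% is relative). The plan should state this and the fitting risk openly.

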We can further characterize baseline incidence of breast symptoms after second-trimester abortion from the placebo and no treatment arms of published randomized clinical trials of pharmacologic methods for lactation suppression. In a three-arm study testing bromocriptine after second-trimester loss or abortion occurring 15-26 weeks gestation, participants were randomized to bromocriptine vs placebo vs no treatment. (Andersen 1990) Utilizing subjective recordings of breast pain and milk secretion, they found the peak breast pain and milk secretion occurred on days 3-7 post-procedure, with only 9% of patients were completely free of breast symptoms in the placebo and no treatment groups.

2C. Emotional distress

In a prior qualitative study of those with a neonatal demise occurring between 19-27 weeks gestation found that they universally did not expect to lactate. (Chen 2015) Prior qualitative work surrounding mid-trimester perinatal loss suggests that breast engorgement and milk leakage causes physical pain and emotional distress. In interviews with 18 individuals with a second trimester perinatal loss or abortion, all reported pain and sensitivity of the breasts between 2nd and 5th day after perinatal loss (Sereshti 2016). Four themes were extracted from the interviews: (1) breast engorgement and leaking was seen as reminder of the loss, (2) it was challenging to reconcile the motherhood identify associated with lactation with the absence of an infant, (3) frustration surrounding lack of knowledge about milk leakage and available remedies, and (4) pain and disability from lactation exacerbating psychological pain from the loss.

2D. Special populations

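### Halving alpha to 0.025 for one interim look leaves part of the 5% unused, and Sections 1 and 5 size the same trial on different alpha, group size and loss

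*Combined protocol and SAP*

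**What the plan says.** Section 5 (Number of Subjects and Statistical Power): "We estimate that 41 subjects in each group are required to show a 30% decrease in those reporting breast symptoms", "with a power of 0.8 and an alpha of 0.025 (planned interim analysis". It then adds: "We plan to recruit 100 subjects, anticipating 10% missing data and loss to follow up". Section 1 (Brief Summary) plans the same 100 participants, the same 30% decrease and the same power of 0.8, but with 32 per group, alpha 0.05 and 30% loss.

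The control rate is given only as a literature range of 50-91%. Section 2B shows where the two ends come from. The lower end is a day-3 figure after loss or abortion at 14-20 weeks, where "50% reported breast tenderness, 45% engorgement, and 20% milk leakage". The upper end is the complement of a trial at 15-26 weeks in which "only 9% of patients were completely free of breast symptoms in the placebo and no treatment groups".

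The hypothesis in Section 3 is directional: "A smaller proportion of those receiving cabergoline will report breast symptoms on Day 4 compared to placebo". No section says whether the test is one- or two-sided, or whether the 30% is in absolute points or relative.

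The Section 6 table marks one interim analysis, in July 2021. Its purpose and boundary are not given. Section 4F says "A DSMC will be formed to monitor the progress of the study", and its only termination rule concerns safety: "any events of stroke, hospitalization for hypertensive emergency, hospitalization for psychiatric condition will lead to immediate termination of the study".

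**The concern.** Two things are at stake.

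First, the two sample-size statements cannot both describe the trial. Each is consistent with its own loss rate, but Section 5's size combined with Section 1's loss leaves too few participants.

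Second, a flat halving of alpha is a costly way to pay for one look. The two test statistics are correlated, so testing each at 0.025 uses less than 5% in total, and much of what is used goes to a look with little information. The final test, where most of the information lies, is held to a stricter threshold than it needs. If the look is not an efficacy test, no alpha needs to be paid at all. As written, a reader cannot tell which p-value would stop the trial in July 2021 or count as success at the end.

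**Working it through.** **Inputs.** From Section 5: power 0.8, alpha 0.025, 41 per group, 100 recruited, 10% loss, control range 50-91%. From Section 1: alpha 0.05, 32 per group, 30% loss. From Section 6: recruitment runs January to June 2021 before the July look, which is 6 months. Enrollment is 19 months in the text (6/19 = 32%) or 15 marked months in the table (6/15 = 40%); 50% is added as a sensitivity.

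**Assumptions not in the documents.** The look tests efficacy; 0.025 applies at both looks; accrual is even; allocation is 1:1; the test is an uncorrected pooled z-test. The drop is absolute unless stated otherwise.

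**Step 1: evaluable patients.** 10% loss: 100 × 0.90 / 2 = 45 per arm. 30% loss: 100 × 0.70 / 2 = 35 per arm. 35 covers Section 1's 32 but not Section 5's 41.

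**Step 2: reproduce 32 and 41.** With d = p1 − p2, s0 = √[2p̄(1−p̄)] and s1 = √[p1(1−p1) + p2(1−p2)], the size per arm is n = (z_α·s0 + z_β·s1)² / d². For 75% to 45%, s0 = √0.48 = 0.693, s1 = √0.435 = 0.660, z_β = 0.842:
- one-sided 0.05: (1.645 × 0.693 + 0.842 × 0.660)² / 0.09 = 31.9, so 32;
- one-sided 0.025: z_α = 1.960 gives 40.7, so 41;
- two-sided 0.025: z_α = 2.241 gives 49.4, so 50.

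One-sided, 55% to 25% gives the same 32 and 41 by symmetry. A two-sided 0.025 test gives about 41 within the cited range only near a control rate of 87-88% (41.3 and 40.3); at 51-79% it needs about 47-52. A relative 30% with a one-sided test also gives both sizes, at a control rate of 88.5% (31.6 and 40.3 before rounding). So 41 reproduces, but its inputs are not unique.

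**Step 3: error used by 0.025 at both looks.** Total error = 1 − P(neither look crosses), from a bivariate normal with correlation √t. At t = 32/40/50%:
- two-sided (c = 2.241): 4.56/4.44/4.28%;
- one-sided (c = 1.960): 4.44/4.32/4.16%.

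**Step 4: power over both looks.** Power = 1 − Φ2(a1, a2; √t), where a1 = (c1·s0 − d√(nt))/s1 and a2 = (c2·s0 − d√n)/s1. The comparator is a Lan-DeMets O'Brien-Fleming-type boundary at overall alpha 0.05 with the same sidedness. Its two-sided final alpha is 0.0500/0.0497/0.0490 at 32/40/50% information. Worked case, two-sided, 75% to 45%, 45 per arm, t = 6/19: with 0.025 at both looks a1 = 0.64, a2 = −0.70 and power is 77.1%; with the O'Brien-Fleming-type boundary it is 83.9%.

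| 45 per arm, absolute 30 points, control 50-91% | 0.025 at both looks | O'Brien-Fleming-type, overall 0.05 | Gain (points) |
|---|---|---|---|
| Two-sided | 75-89% | 82-93% | 4-7 |
| One-sided | 84-94% | 89-96% | 3-6 |

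Per-arm size for 80% power at 75% to 45%: two-sided 48-49 against 41; one-sided 39-40 against 32-33.

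**Step 5: is power below 80%?** At 45 per arm with 0.025 at both looks, the absolute-scale readings that give 41 have about 85% power (one-sided, 55% or 75%) and 85-86% (two-sided, 87-88%). Power is below 80% in other settings:
- two-sided with a control rate of about 50-80%: roughly 75-80%;
- 30% loss, so 35 per arm: even one-sided, 74-80% for control rates up to about 83%;
- a relative 30% with a control rate below the mid-80s: one-sided about 34% at a control rate of 50% and 71-72% at 80%.

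**Step 6: what the O'Brien-Fleming-type boundary costs.** Two-sided, 75% to 45%, 45 per arm, 32-40% information: the chance of stopping early for efficacy falls from about 26-34% to 1-6%. Expected size per arm is 45 × [1 − P(stop) × (1 − t)]. With 0.025 at both looks that is 45 × (1 − 0.26 × 0.68) = 37 at 32% information and 45 × (1 − 0.34 × 0.60) = 36 at 40%; with the O'Brien-Fleming-type boundary it is about 44-45.

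**The case against.** The strongest reply is that a flat 0.025 is valid and that choosing between it and an O'Brien-Fleming-type boundary is a matter of preference: one favours early stopping, the other final power. Validity stands, and so does the trade-off for that boundary. But the trade-off does not justify leaving alpha unused. Keeping 0.025 at the look and spending the remainder at the end gives a two-sided final level of about 0.030-0.034 and gains about 1-3 points with the same chance of stopping early.

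A second reply is that the gain depends on assumptions about the look's purpose and timing and the use of 0.025 at both looks. That is true. If the look is not for efficacy, the comparison of boundaries is moot, but then halving alpha has no purpose either.

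A third reply is that, one-sided, the change relaxes the final test to nearly one-sided 0.05, a weak standard for a trial meant to show clear superiority (Section 4A). That stands as a caution. Sidedness is a separate choice: moving from one-sided 0.025 per look to a two-sided 0.05 O'Brien-Fleming-type design lowers power by about 1-2 points at 45 per arm.

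A reader might infer that the trial is under-powered. The documents do not show this: at control rates of 51-79% a two-sided 0.025 test needs about 47-52 per arm, which does not match the stated 41, and the absolute-scale readings that do match exceed 80%. Equally, a reader might infer that only a two-sided test could fall short. That is not so either, because 30% loss or a relative 30% takes a one-sided test below 80% as well.

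**Conclusion.** The point holds as an inefficiency and an internal conflict. Sections 1 and 5 disagree on alpha (0.05 or 0.025), size (32 or 41 per arm) and loss (30% or 10%); this needs no assumption.

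On the assumptions listed, the flat split controls type I error but leaves about 0.4-0.8 points of the 5% unused (5 − 4.6 to 5 − 4.2). A spending boundary at the same overall alpha and sidedness recovers about 3-7 points of power with maximum recruitment still at 100. Inflated type I error is not a supportable reading. Whether power is adequate cannot be settled until sidedness, control rate, effect scale and loss rate are stated.

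**What to change.** 1. Reconcile Sections 1 and 5 to one alpha, one size per arm and one loss rate. Restate the power with its sidedness, control rate, effect scale (absolute or relative) and test.
2. Say whether the July 2021 look tests efficacy. If it does, replace the flat 0.025 with a boundary at overall alpha 0.05, computed at the actual information fraction. Either use a Lan-DeMets O'Brien-Fleming-type boundary (final two-sided alpha about 0.049-0.050), or keep 0.025 at the look and spend the remaining alpha at the end (final two-sided about 0.030-0.034).
3. If the look is for safety or progress only, say that no efficacy test is done and test the primary outcome at the full 0.05.

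The cost is a few sentences and one boundary calculation, settled before unblinded data are seen. The sponsor has to weigh the lost early stopping and larger expected size under the O'Brien-Fleming-type choice; the alternative in item 2 avoids both, for a smaller gain.
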